3.2 Rationale for study design, doses and control groups

The primary objective of the study is to evaluate the efficacy of multiple infusions of AZD6765iv 50 mg or 100 mg versus placebo when given adjunctively with selected allowed antidepressants (Table 2 and Table 3) for patients with MDD (DSM-IV-TR 296.2x or 296.3x) who exhibited an inadequate response to 3 or more different antidepressant treatments by history. Inadequate response is defined as persistent symptoms that, as judged by the investigator, continue to meet the diagnostic criteria for a MDE according to DSM-IV-TR.

The dose and study design chosen for this study are based on information gained from previous AstraZeneca clinical studies with AZD6765 in MDD, as well as toxicological, pharmacological, and PK studies in different animal species and in vitro human data.

Please see the IB for further information.

An enrollment period of up to 42 days is required to allow the investigator to review the results of laboratory assessments and treatment history reports in support of the ATHF.

4. SUBJECT SELECTION CRITERIA

The patient population should be selected without bias.

Investigator(s) must keep a record of patients who entered pre-study screening, but were never enrolled, eg, patient screening log. Each patient must meet all of the inclusion criteria and none of the exclusion criteria for this study. Under no circumstances can there be exceptions to this rule. The sponsor reserves the right to utilize external representatives to oversee severity of illness determination, diagnosis, and other factors to identify appropriate patient population.

4.1 Inclusion criteria

For inclusion in the study, patients must fulfill the following criteria:

1. Provision of informed consent before initiation of any study-related procedures
2. Patients must provide acceptable proof of identity documentation to confirm initials and date of birth
3. Male and female patients aged 18 to 70 years, inclusive. All male patients who are sexually active must agree to use a double barrier method of contraception (condom with spermicide) from the first dose of IP until 12 weeks after their last dose. All females must have a negative serum pregnancy test. Women of childbearing potential (WOCBP, see below) must use (confirmed by the investigator) a highly effective form of birth control plus the use of a condom by the male sexual partner. The highly effective form of birth control includes: true sexual abstinence, a vasectomized sexual partner, Implanon, female sterilization by tubal occlusion, any

effective IUD/IUS, Depo-Provera™ injections, oral contraceptive, and Evra Patch™ or Nuvaring™. Women should be on a stable method of birth control for a minimum of 3 months as judged by the investigator, prior to randomization and 3 months after the last dose of IP.

Women of non-childbearing potential. Women of non-childbearing potential are defined as women who are either permanently sterilized (hysterectomy, bilateral oophorectomy, or bilateral salpingectomy), or who are postmenopausal. Women will be considered postmenopausal if they are amenorrheic for 12 months prior to randomization without an alternative medical cause. The following age-specific requirements apply:

- Women <50 years old would be considered postmenopausal if they have been amenorrheic for 12 months or more following cessation of exogenous hormonal treatment and follicle stimulating hormone (FSH) levels in the postmenopausal range.
 - Women ≥50 years old would be considered postmenopausal if they have been amenorrheic for 12 months or more following cessation of all exogenous hormonal treatment.
4. Documented clinical diagnosis meeting criteria from the DSM-IV-TR confirmed via the MINI of Major Depressive Disorder: 296.2x MDD, Single Episode or 296.3x MDD, Recurrent.
 5. Currently taking an allowed antidepressant treatment for at least 4 weeks prior to screening. The dose of the antidepressant medications should be as specified in Table 2 and Table 3. All primary and secondary antidepressant treatments must remain at a stable dose and frequency, without clinically significant adjustment. Randomization cannot take place until a minimum adequate duration of stable treatment, as specified in Table 2 and Table 3, has been achieved.
 6. HAM-D-17 score ≥24, CGI-S ≥5, and QIDS-SR-16 ≥19 at screening, and Visit 2/randomization
 7. Lifetime history of inadequate response, as described in Section 3.1, to at least 3 trials of antidepressant treatment of adequate dose and duration as specified in Table 1, Table 2, and Table 3. One of these trials must be the current treatment trial.
 8. Be able to understand and comply with the requirements of the study, as judged by the investigator
 9. Outpatient status at screening and enrollment (randomization) visits
 10. Capable of returning for study-related assessments, as judged by the investigator

For inclusion in the optional exploratory genetic sample collection, patients must fulfill the following criterion:

1. Provision of informed consent for genetic research

If a patient declines to participate in the optional genetic component of the study, there will be no penalty or loss of benefit to the patient. The patient will not be excluded from other aspects of the study described in this CSP, so long as they consent.

4.2 Exclusion criteria

Patients must not enter the study if any of the following exclusion criteria are fulfilled:

1. Involvement in the planning/or conduct of the study (applies to both AstraZeneca staff and/or staff at the study site)
2. Previous enrollment in the present study
3. Patients who are currently participating in another clinical study in which the patient is exposed to an investigational or non-investigational drug or device, or have done so within the last 30 days prior to screening for studies unrelated to MDD, or 6 months for studies related to MDD.
4. Patients who have no regular contact with an adult who could come to the patient's aid should an urgent need arise. This excludes patients who are undomiciled or who do not have at least one adult with whom there is regular contact.
5. Patients with a history of DSM-IV-TR diagnosis of bipolar disorder or schizophrenia or schizoaffective disorder or currently exhibiting psychotic features associated with their depression; dementia or suspicion thereof, is also exclusionary. Other DSM-IV-TR Axis I disorders are permitted as long as they are not considered primary disorders.
6. Patients who during the past two years have met DSM-IV-TR diagnostic criteria for post-traumatic stress disorder.
7. Currently being treated with MAOIs, depakote, carbamazepine, lamotrigine, topiramate, opiates, memantine, barbiturates, or bupropion >300 mg per day (see [Table 6](#) for details and additional prohibited medications)
8. ECT, VNS, or TMS, or previous treatment with ketamine infusion within the 6 months prior to randomization, or any history of deep brain stimulation
9. Substance abuse or dependence within the 6 months prior to screening. Patients with a positive urine drug screen (UDS) for methamphetamines benzodiazepines, cocaine and/or metabolites, amphetamines, tetrahydrocannabinol (THC), opiates, PCP, ethanol, methaqualone (South Africa only), and barbiturates will be excluded

except for patients testing positive for prescribed medications **that are otherwise permitted and there is no evidence of misuse, abuse, or dependence**. Patients can be re-tested only if either the initial THC, opiate, or barbiturate result is positive and they have a prescription, but the patient should be excluded if the result is still positive for THC, opiate, or barbiturate, respectively, at the second test. Patients with positive UDS for a drug(s) legally available by prescription must provide evidence of prescription for the drug(s).

10. Patients with a DSM-IV-TR Axis II disorder, which in the opinion of the investigator, has a major impact on the patient's current psychiatric status
11. Systolic BP <85 or >160 mmHg or diastolic BP >95 mmHg or heart rate <50 or >105 beats per minute at screening or randomization. Exclusionary values may be repeated once.
12. QTcF (Fridericia-corrected) \geq 450 msec at screening (Visit 1) or randomization
13. Patients who have had a suicide attempt within the last 6 months. Patients who, in the investigator's judgment, pose a significant suicide risk. Evidence of significant suicide risk may include any history of suicidal behavior and/or any suicidal ideation of type 4 or 5 on the C-SSRS in the last 6 months at screening or randomization.
14. Patients who are pregnant or lactating
15. Patients with unstable or inadequately controlled medical conditions (eg, unstable angina) or evidence of clinically relevant disease, eg, renal or hepatic impairment, symptomatic or significant coronary artery disease, cerebrovascular disease, viral hepatitis B or C, syphilis, or acquired immunodeficiency syndrome (AIDS). Hypothyroidism is permitted if corrected and the patient is on a stable treatment regimen for a minimum of 6 months. Combination of abnormal thyroid-stimulating hormone (TSH) test results and abnormal free thyroxine levels require discussion with Sponsor or Sponsor's representative.
16. Patients with diabetes mellitus fulfilling any of the following criteria:
 - Unstable diabetes mellitus defined as glycosylated hemoglobin (HbA_{1c}) >8.5% at screening
 - Admitted to hospital for treatment of diabetes mellitus or diabetes mellitus-related illness in the past 12 weeks
 - Not under physician care for diabetes mellitus

- Has not been on the same dose of oral hypoglycaemic drug(s) and/or diet for the 4 weeks prior to screening. For thiazolidinediones (glitazones) this period should not be less than 8 weeks.
17. Patients whose depression is secondary to an organic or medical cause or first presented after the age of 60 years
 18. Patients with any history of seizure disorder (except for febrile seizures in childhood)
 19. Clinically significant laboratory value that signifies a major medical illness that is inadequately controlled in the judgment of the investigator: Patients with laboratory values outside normal limits, but not judged to be clinically significant may be randomized. However, such laboratory parameters should be followed. Examples of clinically significant laboratory values that would require exclusion include: alanine aminotransferase (ALT) or aspartate aminotransferase (AST) ≥ 3.0 times the upper limit of normal (ULN) or total bilirubin ≥ 1.2 times the ULN (unless documented Gilbert's syndrome).
 20. Previous exposure to AZD6765
 21. Currently hospitalized at screening
 22. Current diagnosis of sleep apnea
 23. Body mass index (BMI) ≥ 45 kg/m²

For the patient to be qualified for the optional genetic research, the patient must not have had:

1. Previous allogeneic bone marrow transplant
2. Non-leukocyte depleted whole blood transfusion within 120 days prior to the date of genetic sample collection

If either of these 2 exclusion criteria is present, the patient cannot participate in the optional genetic research.

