At Visit 1 and again before randomization at Visit 2, assessments will be conducted to ensure that the HAM-D-17 is ≥ 24 , CGI-S is ≥ 5 , and QIDS-SR-16 is ≥ 19 . The HAM-D-17 and a review of the patient’s prior antidepressant therapy will also be conducted prior to randomization and after medical clearance. If the patient does not meet the study entry criteria at Visit 2, the patient will be considered a screen failure and will not be randomized to the study. Patients who qualify will receive baseline clinical assessments of MADRS, HAM-A, S-STS, and CogState, and be randomly assigned in a 1:1:1 ratio to 1 of the 3 treatment arms:

- **Treatment A:** AZD6765iv 50 mg (AZD6765 Solution for Infusion, 0.5 mg/mL) by iv infusion
- **Treatment B:** AZD6765iv 100 mg (AZD6765 Solution for Infusion, 1.0 mg/mL) by iv infusion
- **Treatment C:** Placebo (0.9% sodium chloride [normal saline] solution for injection) by iv infusion

Patients will receive multiple infusions of AZD6765iv 50 mg or 100 mg, or placebo saline during the 12-week study treatment period and must be treated as outpatients during the entire course of the study. Patients will undergo the study procedures and assessments at designated visits per the study assessments (Table 4). Patients will be encouraged to eat and drink within 4 hours prior to infusion to reduce the risk of orthostatic hypotension.

The patient's depression and suicidality (suicide risk) will be assessed by the following instruments: Mini-International Neuropsychiatric Interview (MINI) (at screening), QIDS-SR-16, HAM-D-17 (screening and randomization only), MADRS, Columbia-Suicide Severity Rating Scale (C-SSRS), HAM-A, S-STS, CGI-S, and CGI-I. Dissociative symptoms will be assessed by Clinician Administered Dissociative States Scale (CADSS). The patient's quality of life will be assessed by the self-reported SDS. Cognitive functioning will be assessed using a battery of 4 tests of CogState ClinicalTrials (CogState, Ltd., New Haven, CT). A HAM-D-17 and a review of the patient's prior antidepressant treatment will be conducted after medical clearance and prior to randomization. After randomization, clinical measures to be conducted prior to infusion include QIDS, MADRS, HAM-A, S-STS, SDS, CGI-S, CGI-I and CogState. Measures to be collected after infusion include C-SSRS and CADSS.

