6.2.1.2 Randomization visit (Visit 2)

Prior to the randomization visit, adequate documentation must be in place to confirm that the patient meets modified ATHF inclusion criteria of inadequate response to at least 2 previous antidepressant treatments of adequate dose and duration. In addition, results from all laboratory assessments conducted at the screening visit should be available and confirm that the patient continues to meet clinical and safety criteria for inclusion.

At the randomization visit, the QIDS-SR-16 will be administered first. Prior to conducting any further procedures, the QIDS-SR-16 should be scored (without review by the investigator) and if the inclusion criterion score of ≥ 19 is not met, no further study procedures are to be conducted and the patient will not be randomized. At no time may the patient be informed of the inclusion criterion score on the QIDS-SR-16. If the QIDS-SR-16 criterion is met, the HAM-D-17 interview will be conducted and the CGI-S will be completed to determine whether the patient meets the inclusion criteria of a HAM-D-17 total score ≥ 24 and CGI-S ≥ 5 . If these criteria are not met, no further procedures are to be conducted and the patient will not be randomized. If these criteria are met, the patient is randomized and the remaining clinical and laboratory assessments are conducted in accordance with Table 4.

The MADRS, CGI-S, S-STS, HAM-A, SDS, and Cogstate are conducted prior to the first infusion. After the first (and last) infusion, the patient must remain in the clinic for at least 3 hours after the infusion (T_4) during which time AEs are collected, and CADSS and C-SSRS are administered. Vital signs and orthostatic BP are measured at every infusion at multiple time points: T_0 , T_1 (vital signs only), and either at least 1 hour (T_2) after the end of infusion (all indicated visits, except for Visits 2 and 16), or, at least 3 hours (T_4) after the end of infusion (applies to Visits 2 and 16, which corresponds to first and last infusions).

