6.2.2.2 Sheehan Suicide Tracking Scale (S-STs) Self report form

The S-STs is a prospective, patient self-report or clinician-administered rating scale that tracks suicidal ideation and behaviors and has been shown to be sensitive to clinical change with treatment ([Coric et al 2009](#), [Khan et al 2011](#)).

Only the self-report portion of the scale will be used in this study, which must be reviewed and signed by the investigator prior to conducting the C-SSRS interview. The S-STs will be administered at designated visits prior to the infusion. Note that the C-SSRS should be administered after the infusion.

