6.2.2.6 Columbia-Suicide Severity Rating Scale (C-SSRS)

The C-SSRS is a unique, simple and short method of assessing both behavior and ideation that tracks all suicidal events, and provides a summary of suicidality (Posner et al 2007). It assesses the lethality of attempts and other features of ideation (frequency, duration, controllability, reasons for ideation and deterrents), all of which are significantly predictive of completed suicide. The C-SSRS must be administered after each infusion and prior to discharging the patient from the clinic.

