6.3 Efficacy

6.3.1 Sequence of clinical rating assessments

Table 4 lists all clinical and laboratory assessments to be conducted at the screening visit and all subsequent visits. The following “priority order” among clinical ratings will be in effect for all visits after the screening visit.

Pre-infusion

- QIDS-SR-16
- S-STS (self report)
- MADRS
- HAM-A
- SDS
- CGI-S
- CGI-I
- CogState

Post-infusion

- C-SSRS (conducted by the investigator after reviewing and signing S-STS during visits when both instruments are used)
- CADSS

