6.4.9.6 Columbia-Suicide Severity Rating Scale (C-SSRS)

The C-SSRS is a unique, simple and short method of assessing both behavior and ideation that tracks all suicidal events, and provides a summary of suicidality (Posner et al 2007). It assesses the lethality of attempts and other features of ideation (frequency, duration, controllability, reasons for ideation and deterrents), all of which are significantly predictive of completed suicide.

The C-SSRS will be administered at the screening visit and at each scheduled visit throughout the study by a trained rater. The trained rater will record the clinical observation on the scale, which will be used as the source document. If at all possible, the same individual should perform the assessment at each visit to reduce scoring variability. In the event the primary rater is not available, a designated back-up rater who meets the same qualifications may perform the C-SSRS.

The C-SSRS must be administered at designated visits after the infusion.

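### Criterion 13 relies on a C-SSRS at randomization, but the Visit 2 C-SSRS is done only after randomization and the first infusion

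*Protocol*

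**What the plan says.** Criterion 13 in Protocol Section 4.2 excludes patients with a suicide attempt in the last 6 months and patients whom the investigator judges to pose a significant suicide risk. Among the evidence that may support that judgment it names "any suicidal ideation of type 4 or 5 on the C-SSRS in the last 6 months at screening or randomization". Sections 4 and 5.3 allow no exceptions to the eligibility criteria, and Table 4 schedules an eligibility check at both Visit 1 and Visit 2.

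Section 6.2.1.2 sets the order at Visit 2: the QIDS-SR-16, then the HAM-D-17 and CGI-S. It continues: "If these criteria are met, the patient is randomized and the remaining clinical and laboratory assessments are conducted". The ratings it lists before the first infusion (MADRS, CGI-S, S-STS, HAM-A, SDS, CogState) do not include the C-SSRS. That comes in the stay of at least 3 hours after the infusion, "during which time AEs are collected, and CADSS and C-SSRS are administered".

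Other sections agree:
- Section 3.1: "Measures to be collected after infusion include C-SSRS and CADSS".
- Section 6.2.2.6: "The C-SSRS must be administered after each infusion and prior to discharging the patient from the clinic".
- Section 6.4.9.6: "The C-SSRS must be administered at designated visits after the infusion".
- Section 6.3.1 lists the C-SSRS as post-infusion in an order that applies to every visit after screening, so it includes Visit 2.

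**The concern.** The criterion names a piece of evidence for the eligibility decision, and the visit schedule produces that evidence only after the decision has been made and the drug given. The patients are severely depressed outpatients (HAM-D-17 of at least 24, CGI-S of at least 5), and screening can last up to 42 days, so suicidal ideation may change between the two visits.

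A site that keeps to the written order could randomize and infuse a patient, then record type 4 or 5 ideation the same day. That patient would fall under the on-study referral rule in Section 6.4.3 and would not have been assessed for exclusion on that finding.

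A smaller issue concerns reporting. Section 3.1.2 defines baseline as what is assessed before randomization, so the C-SSRS baseline is the screening record. Section 11.2.6.1 then counts ideation at any post-baseline evaluation.

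**Working it through.** The protocol states no figure to reproduce. The check compares the C-SSRS timing statements and counts administrations.

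**1. Is there a C-SSRS before randomization at Visit 2?** Section 6.2.1.2 makes randomization conditional on three scales, none of them the C-SSRS, and puts the C-SSRS after the infusion. Sections 3.1, 6.2.2.6, 6.3.1 and 6.4.9.6 agree. In Table 4, the footnote requiring administration before any infusion is attached to seven other ratings and not to the C-SSRS. No second, pre-dose C-SSRS is scheduled. The only one before dosing is the baseline version completed at screening (Section 6.2.1.1).

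**2. Does another instrument fill the gap at Visit 2?**
- HAM-D-17: its suicide item (Section 6.2.2.3) is rated before randomization and can be used.
- QIDS-SR-16: it has a suicidal ideation item (Section 6.2.2.1), but Section 6.2.1.2 has it scored without investigator review before the decision.
- S-STS: the patient completes it before the infusion. Section 6.2.2.2 requires only a form "which must be reviewed and signed by the investigator prior to conducting the C-SSRS interview", and that interview follows the infusion.

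So no dedicated suicidality instrument has to be reviewed by the investigator before dosing at Visit 2. At screening, Section 6.2.1.1 does put both the S-STS review and the C-SSRS before the enrolment decision.

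**3. Comparison with similar criteria.** Criteria 11 (blood pressure, heart rate) and 12 (QTcF) are also applied at screening or randomization. Both have a pre-infusion (T0) measurement at Visit 2 (Table 4 footnotes, Table 8). The C-SSRS has none.

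**4. Counts.**
- Table 4, C-SSRS row: 1 (screening) + 15 (Visits 2 to 16) + 1 (follow-up) = 17 per patient.
- Before the first dose: 1 of 17.
- Greatest age of that record: screening may start 42 days before Day 1 (Section 3.1.1), so up to 42 days.

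**5. Effect on the C-SSRS summary.** The protocol does not state the recall period of the Visit 2 form. If it asks about the time since the last visit, ideation arising between screening and the first dose would count as post-baseline under Section 11.2.6.1. If it asks only about the time since the infusion, it would not.

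**The case against.** Five points can be made against this.

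- **The phrase may only date the 6-month look-back.** Table 6 uses similar wording that way for ketamine and for brain stimulation. Even so, applying the look-back at randomization needs C-SSRS information current at randomization, and the only record then available is the screening one.
- **The C-SSRS item is not an automatic cut-off.** This stands. The operative test is the investigator's judgment, and the attempt history, the screening C-SSRS and the HAM-D-17 suicide item can all inform it at Visit 2. What fails is one named piece of evidence, and it is the most specific one for that day.
- **Section 3.1.2 says that Day 1 assessments come before randomization, and the C-SSRS row of Table 4 has no post-infusion footnote, although the CADSS row does.** The general sentence cannot hold for every Visit 2 item, since the CADSS and the end-of-infusion ECG follow the dose. The instructions specific to the C-SSRS are explicit and repeated. At most this adds a second conflict for sites to resolve.
- **The comparison with criteria 11 and 12 is imperfect.** T0 means before the infusion, not necessarily before randomization, and a literal reading of Section 6.2.1.2 would put those measurements after randomization too. That is fair. The comparison shows only that those criteria have a pre-dose value at Visit 2.
- **The consequences are limited.** Also fair. The C-SSRS is still done before discharge, so exposure before detection is one supervised infusion, and Section 6.4.3 provides for referral.

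**Conclusion.** The contradiction is real and should be fixed. Under the order as written, the randomization-day C-SSRS named in criterion 13 cannot inform eligibility, and the last C-SSRS before the first dose may be up to 42 days old. This rests on the specific post-infusion instructions prevailing over the general sentence in Section 3.1.2.

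It is a correction to a safety eligibility rule. It does not touch the primary analysis, and the exclusion threshold is not in question. Dated adverse events and the treatment-emergent definition in Section 11.2 still separate pre-dose from later events. Only the descriptive C-SSRS summary could be affected, and only if the Visit 2 form looks back beyond the infusion. The number of patients affected cannot be derived from the protocol.

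**What to change.** At Visit 2, before randomization, administer the C-SSRS covering the time since screening, and have the investigator review the S-STS. Use that C-SSRS for criterion 13 and as the C-SSRS baseline. Keep the post-infusion C-SSRS, limited to the time since the pre-randomization one. Amend Sections 6.2.1.2, 6.2.2.2, 6.2.2.6, 6.3.1 and 6.4.9.6 and Table 4 to match, and align the general statement in Section 3.1.

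The cost is one short interview per patient, 18 scheduled instead of 17, by a trained rater already on site. Over all randomized patients that is 1 × 282 = 282 extra interviews, plus one for any patient who then fails at Visit 2. Because this edition already provides for patients who have finished their infusions, the count among patients still to be randomized would be lower. The pre-infusion part of Visit 2 becomes slightly longer.
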